ECOG	Eastern Cooperative Oncology Group
EDTA	ethylenediaminetetraacetic acid
EE	Efficacy-Evaluable
EFS	Event free survival
EMEA	European Agency for Evaluation of Medicinal Products
FAB	French-American-British classification
FDA	Food and Drug Administration
FISH	fluorescent in situ hybridization
FWA	Federal wide assurance

GCP	Good Clinical Practice
G-CSF	Granulocyte colony stimulating factor, filgrastim (Neupogen)
GM-CSF	Granulocyte/macrophage colony stimulating factor, sargramostim, (Leukine, Prokine)
HDACs	Histone deacetylases
HHS	Department of Health and Human Services'
HI	Hematologic improvement
HIV	Human Immunodeficiency Virus
HRPO	Human Research Protection Office (IRB)
ICH	International Conference on Harmonization
IFN	Interferon
IL-2	Interleukin-2
IND	Investigational New Drug
IRB	Institutional Review Board
ITT	Intent-to-treat
IV	Intravenous (i.v.)
IVRS	Interactive Voice Response System
IWG	International Working Group
LD	Longest diameter
LDH	Lactate dehydrogenase
LPS	lipopolysaccharide
MCH	Mean corpuscular hemoglobin
MCHC	Mean corpuscular hemoglobin concentration
MCL	Mantle cell lymphoma
MCV	Mean corpuscular volume
MDS	Myelodysplastic syndrome
MedDRA	Medical Dictionary for Regulatory Activity
MM	Multiple myeloma
MRI	Magnetic resonance imaging
MTD	Maximum tolerated dose
NCCN	National Cancer Center Network
NCI	National Cancer Institute
NIH	National Institutes of Health
NK	Natural killer cell
NSCLC	Non-small cell lung cancer
OHRP	Office of Human Research Protections
ORR	Overall response rate
OS	Overall survival
PB	Peripheral blood
PBMC	Peripheral blood mononuclear cell
PD	Progressive disease
PI	Principal investigator

PR	Partial response (Partial remission)
PSA	Prostate-specific antigen
QASMC	Quality Assurance and Safety Monitoring Committee
RAEB	Refractory anemia with excess blasts
RAEB-t	Refractory anemia with excess blasts in transformation
RARS	Refractory anemia with ringed sideroblasts
RBC	Red blood cell (count)
RECIST	Response Evaluation Criteria in Solid Tumors (Committee)
RFS	Relapse free survival
RR	Response rate
SAE	Serious adverse event
SCC	Siteman Cancer Center
SCT	Stem cell transplant
SD	Stable disease
TF	Treatment failure
TPP	Therapeutics Product Programme
TRAIL	TNF-related apoptosis-inducing ligand
TSH	Thyroid stimulating hormone
TTP	Time to progression
UPN	Unique patient number
US	Ultrasound
VEGF	Vascular endothelial growth factor
VPA	Valproic acid
WBC	White blood cell (count)
FCBP	Females of child bearing potential

1.0 BACKGROUND AND RATIONALE

1.1 The Mammalian Target of Rapamycin (mTOR) Pathway

Activation of the mammalian target of rapamycin (mTOR) pathway has been implicated in the development of several malignancies.^{1,2} A member of the phosphatidylinositol 3-kinase (PI3K)-related family of kinases, mTOR is a 289-kDa protein serine/threonine kinase that was first identified as the cellular target of rapamycin and is involved in checkpoint regulation of the cell cycle regulation. Additionally, the mTOR pathway is responsible for upregulating downstream signaling of hypoxia inducible factor-1- α (HIF1- α) which promotes angiogenesis and cell proliferation.³ mTOR is represented by two structurally and functionally distinct multiprotein signaling complexes, the rapamycin sensitive mTOR complex 1 (mTORC1), and rapamycin insensitive mTOR complex 2 (mTORC2). mTORC 1 is mainly activated via the PI3K pathway through AKT and the tuberous sclerosis complex (TSC1/TSC2). Activated AKT phosphorylates TSC2, which leads to dissociation of TSC1/TSC2 complex, thus inhibiting the ability of TSC2 to act as a GTPase activating protein. This allows Rheb, a small G-protein, to remain in a GTP bound state and to activate mTORC1. Another regulator of the mTOR pathway is NF1.

1.2 Everolimus

Everolimus is a novel oral derivative of rapamycin. At the cellular and molecular level, everolimus acts as a signal transduction inhibitor, and selectively inhibits mTOR. Everolimus has been in clinical development since 1996 as an immunosuppressant in solid organ transplantation and has been in development for patients with various malignancies since 2002. It has been demonstrated to have activity in several human solid tumor cell lines, as well as in mouse xenograft models.⁴⁻⁷ Everolimus was first approved by the U.S. Food and Drug Administration (FDA) for the treatment of patients with advanced renal cell carcinoma (RCC) in 2009. It recently received approval for use in patients with advanced pancreatic neuroendocrine tumors as well. The FDA approved dose of everolimus is 10 mg daily by mouth. Everolimus is extensively metabolized in the liver and eliminated by bile. It is a substrate of CYP3A4 and substrate and inhibitor of P-glycoprotein. It well tolerated, with the most common adverse reactions being stomatitis, fatigue, nausea, diarrhea. Grade 3-4 adverse reactions ($\geq 2\%$) include infections, stomatitis, fatigue and pneumonitis. The most common laboratory abnormalities are anemia, hypercholesterolemia, hypertriglyceridemia, hyperglycemia, lymphopenia and increased creatinine.⁸

[Redacted]

[10-12](#)

1.2.1 Overview of Everolimus

[Redacted]

[Redacted]

[Redacted]

[figure not shown]
[Redacted]

1.2.2 mTOR Pathway and Cancer

At the cellular and molecular level, everolimus acts as a signal transduction inhibitor. It selectively inhibits mTOR (mammalian target of rapamycin), a key protein kinase which regulates cell growth, proliferation and survival. The mTOR kinase is mainly activated via the phosphatidylinositol 3-kinase (PI3-Kinase) pathway through AKT/PKB and the tuberous sclerosis complex (TSC1/2). Mutations in these components or in PTEN, a negative regulator of PI3-kinase, may result in their dysregulation. Abnormal functioning of various components of the signaling pathways contributes to the pathophysiology of numerous human cancers. Various preclinical models have confirmed the role of this pathway in tumor development ([Cohen et al 2005](#)).

The main known functions of mTOR include the following ([Bjornsti and Houghton 2004](#)):

- mTOR functions as a sensor of mitogens, growth factors and energy and nutrient levels;
- Facilitating cell-cycle progression from G1-S phase in appropriate growth conditions;
- The PI3K/mTOR pathway itself is frequently dysregulated in many human cancers, and oncogenic transformation may sensitize tumor cells to mTOR inhibitors;
- PI3-kinase mutations have been reported in the primary tumor in 10-20% of human colorectal cancers ([Frattini 2005](#), [Velho 2005](#));
- The loss of PTEN protein, either through gene deletion or functional silencing (promoter hypermethylation), is reported in approximately 60% of primary human colorectal cancers ([Goel et al 2004](#));
- The mTOR pathway is involved in the production of pro-angiogenic factors (i.e., VEGF) and inhibition of endothelial cell growth and proliferation;
- Through inactivating eukaryotic initiation factor 4E binding proteins and activating the 40S ribosomal S6 kinases (i.e., p70S6K1), mTOR regulates protein translation, including the HIF-1 proteins. Inhibition of mTOR is expected to lead to decreased expression of HIF-1.

[Redacted]

1.3 Next Generation Sequencing

TSC1, TSC2, NF1, NF2, and STK11 mutational analysis will be performed as part of a larger panel of genomic testing to aid in treatment of patients with cancer as standard of care and will not be billed to Novartis. This screening will identify potential patients for this study. Provided they meet other eligibility criteria, they will be consented to participate in the study.

Genes to be sequenced include TSC1, TSC2, NF1, NF2 and STK11. The technology employed will permit detection of single nucleotide variants, small insertions, deletions, and complex indels, as well as amplifications and large deletions across the coding regions of all sequenced genes. Tumor-derived DNA obtained from formalin fixed, paraffin embedded tissue will serve as the source of input material for the assay. Sensitive and specific methods to call variants and other genomic alterations will be performed using a clinical grade data analysis pipeline including a software package allowing for interpretation and reporting of such findings.

1.4 Study Rationale

Cancer is a molecularly heterogeneous disease comprised of complex genomic alterations in common and overlapping pathways. Complicating the heterogeneous nature of cancer is the clonal evolution that occurs within a tumor¹⁰. The molecular landscape of the tumor at time of diagnosis may differ significantly from the molecular profile at the time of disease progression¹¹. It is critical that tumor samples are obtained at the time of diagnosis and following disease progression. Key alterations in the tumor biology can be identified efficiently through use of routine next generation sequencing. It is important to identify predictive biomarkers for response to molecularly targeted agents; however, it is also important to investigate biomarkers that confer resistance to specific therapies. As an example, 10% of non small cell lung cancers (NSCLC) carry activating mutations in the epidermal growth factor receptor tyrosine kinase (EGFR TK).¹² Although tyrosine kinase inhibitors such as erlotinib have demonstrated response rates of approximately 70-90%^{13,14}, drug resistance eventually develops as a consequence of an emergence of a population of tumor cells harboring a new mutation in the EGFR TK domain or amplification in the MET oncogene¹⁵. As a result, clinical studies are underway targeting EGFR mutations in combination with MET inhibitors to target the genomic alterations that are occurring at the time of progression on an EGFR inhibitor. Using a similar model, mutations in the mTOR/PI3K pathway and potential mechanisms of resistance to everolimus can be identified using routine next generation sequencing at the time of diagnosis and at time of disease progression.

2.0 OBJECTIVES

2.1 Primary Objectives

To assess the response rate of patients with solid malignancies whose tumors carry mutations in TSC1, TSC2, NF1, NF2, or STK11 to everolimus.

2.2 Secondary Objectives

1. To correlate mutations in the mTOR pathway with therapeutic response to everolimus.
2. To investigate the genetic changes associated with disease progression following treatment with everolimus.

3.0 PATIENT SELECTION

3.1 Inclusion Criteria

1. Histologically confirmed diagnosis of advanced (metastatic, recurrent, or unresectable) cancer with mutations in any of the following genes: TSC1, TSC2, NF1, NF2 or STK11
2. Must have failed at least 1 standard of care systemic therapy for their malignancy.
3. Measurable disease defined as lesions that can be accurately measured in at least one dimension (longest diameter to be recorded) as ≥ 10 mm with CT scan, as ≥ 20 mm by chest x-ray, or ≥ 10 mm with calipers by clinical exam.
4. Prior therapy (chemotherapy, radiation therapy, and surgery) is allowed if completed at least 2 weeks prior to registration and if all treatment-related toxicities are resolved to \leq CTCAE grade 1, with the exception of alopecia and hematologic values otherwise meeting the bone marrow function criteria specified below.
5. At least 18 years of age.
6. ECOG performance status ≤ 2 (see Appendix A).
7. Normal bone marrow and organ function as defined below:
 - a. Leukocytes $> 3,000/\text{mcL}$
 - b. Absolute neutrophil count $> 1,500/\text{mcL}$
 - c. Platelets $> 100,000/\text{mcL}$
 - d. Hemoglobin > 9.0 g/dL
 - e. Total serum bilirubin ≤ 2.0 x IULN
 - f. AST(SGOT)/ALT(SGPT) ≤ 2.5 x IULN (≤ 5.0 x IULN in patients with liver metastases)

- g. Serum creatinine $\leq 1.5 \times$ IULN OR creatinine clearance > 45 mL/min/1.73 m² for patients with creatinine levels above institutional normal
 - h. Fasting cholesterol ≤ 300 mg/dL OR ≤ 7.75 mmol/L AND fasting triglycerides $\leq 2.5 \times$ IULN. NOTE: In case one or both of these thresholds are exceeded, the patient can only be included after initiation of appropriate lipid lowering medication
8. Able to swallow tablets.
 9. Women of childbearing potential, defined as all women physiologically capable of becoming pregnant, must use highly effective methods of contraception (please refer to Section 5.4) during the study and for 8 weeks after. Women are considered post-menopausal and not of childbearing potential if they have had 12 months of natural (spontaneous) amenorrhea with an appropriate clinical profile (e.g., age appropriate, history of vasomotor symptoms) or have had surgical bilateral oophorectomy (with or without hysterectomy) or tubal ligation at least six weeks prior to randomization. In the case of oophorectomy alone, only when the reproductive status of the woman has been confirmed by follow-up hormone level assessment is she considered not of childbearing potential.
 10. Male patients whose sexual partner(s) are women of childbearing potential must agree to use adequate contraception during the study and for 8 weeks after the end of treatment.
 11. Able to understand and willing to sign an IRB approved written informed consent document (or that of legally authorized representative, if applicable)

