5.2.8 Management of hyperlipidemia and hyperglycemia

Severity	Everolimus Dose Adjustment and Management Recommendations
Grade 1	No dose adjustment required. Initiate appropriate medical therapy and monitor.
Grade 2	No dose adjustment required. Manage with appropriate medical therapy and monitor.
Grade 3	Temporary dose interruption. Re-initiate everolimus at lower dose. Manage with appropriate medical therapy and monitor.
Grade 4	Discontinue everolimus and treat with appropriate medical therapy.

Treatment of hyperlipidemia should take into account the pre-treatment status and dietary habits of the patient. Grade 2 or higher hypercholesterolemia (>300 mg/dL or 7.75 mmol/L) or grade 2 hypertriglyceridemia or higher (>2.5x upper normal limit) should be treated with a 3-hydroxy-3-methyl-glutaryl (HMG)-CoA reductase inhibitor (e.g. atorvastatin, pravastatin, fluvastatin) or appropriate triglyceride-lowering medication, in addition to diet.

Note: Concomitant therapy with fibrates and an HMG-CoA reductase inhibitor is associated with an increased risk of a rare but serious skeletal muscle toxicity manifested by rhabdomyolysis, markedly elevated creatine phosphokinase (CPK) levels and myoglobinuria, acute renal failure and sometimes death. The risk versus benefit of using this therapy should be determined for individual patients based on their risk of cardiovascular complications of hyperlipidemia.

Dyslipidemia (including hypercholesterolemia and hypertriglyceridemia) has been reported in patients taking everolimus. Monitoring of blood cholesterol and triglycerides prior to the start of everolimus therapy and periodically thereafter as well as management with appropriate medical therapy is recommended.

Hyperglycemia has been reported in patients taking everolimus. Monitoring of fasting serum glucose is recommended prior to the start of everolimus and periodically thereafter. More frequent monitoring is recommended when everolimus is co-administered with other drugs that may induce hyperglycemia. Optimal glycemic control should be achieved before starting a patient on everolimus.

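### Inclusion item 7h lets a patient whose lipids are still at grade 4 start everolimus, because its note asks for lipid-lowering medication but no repeat value or ceiling

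*Combined protocol and SAP*

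**What the plan says.** Section 3.1, item 7h, sets the two fasting lipid limits (300 mg/dL, or 7.75 mmol/L, for cholesterol; 2.5 x IULN for triglycerides) and then the exception: "NOTE: In case one or both of these thresholds are exceeded, the patient can only be included after initiation of appropriate lipid lowering medication".

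Section 5.2.8 uses the same figures to say when lipid treatment is needed during the study: "Grade 2 or higher hypercholesterolemia (>300 mg/dL or 7.75 mmol/L) or grade 2 hypertriglyceridemia or higher (>2.5x upper normal limit"). Its table then sets the action by severity. The strictest row, for grade 4, reads "Discontinue everolimus and treat with appropriate medical therapy". One step down, at grade 3, the drug is paused and may be resumed: "Temporary dose interruption. Re-initiate everolimus at lower dose. Manage with appropriate medical therapy and monitor". The row for grade 2 leaves the dose alone: "No dose adjustment required. Manage with appropriate medical therapy and monitor".

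On testing, section 5.2.8 recommends "Monitoring of blood cholesterol and triglycerides prior to the start of everolimus therapy and periodically thereafter", together with medical management. The study calendar (section 10.0) marks the lipid panel at screening only. Footnote 5 leaves later panels to the treating physician. Baseline evaluations may be up to 14 days old at the start of therapy.

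Sections 5.0 and 5.1 set the starting dose at 10 mg daily, with no lower dose for raised baseline lipids.

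**The concern.** Items 7a to 7g each require a laboratory value to be met, including where an alternative limit is offered (transaminases with liver metastases, creatinine clearance). Item 7h alone can be satisfied without any lipid value being reached. A patient already on lipid medication and still above the limits appears to meet the note at once.

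What is at stake is patient safety. Section 1.2 lists hypercholesterolemia and hypertriglyceridemia among the most common laboratory abnormalities with everolimus. Under the entry rule as written, a patient could take a first full dose at a lipid grade where the protocol's own table would stop the drug. No result would be on file to show that the lipid medication had worked.

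**Working it through.** No arithmetic applies, so the check sets the provisions side by side.

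**1. Entry condition above the limits.** Item 7h requires only that appropriate medication has been initiated. The lipid value after that does not enter the condition.

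**2. Grades covered.** The limits in item 7h (300 mg/dL; 2.5 x IULN) are the ones section 5.2.8 gives as the start of grade 2 or higher. The exception is open above those limits, so it covers grades 2, 3 and 4.

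**3. Entry against on-treatment handling.**

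| Lipid grade | Entry under the 7h note, once medicated | Section 5.2.8, on treatment |
|---|---|---|
| 2 | allowed, 10 mg | dose kept, medical therapy |
| 3 | allowed, 10 mg | interrupt, restart lower; no recovery level named |
| 4 | allowed, 10 mg | discontinue |

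Grade 2 agrees. Grade 3 differs, but section 5.2.8 lets the patient resume and names no lipid value for doing so. Grade 4 is the clear mismatch.

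**4. Does another provision close the grade 4 case?**

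- *Inclusion item 4* allows prior therapy "if completed at least 2 weeks prior to registration and if all treatment-related toxicities are resolved to" CTCAE grade 1 or lower. This keeps out lipid toxicity caused by earlier treatment. It does not reach pre-existing or unrelated dyslipidemia.
- *Exclusion item 10* (uncontrolled intercurrent illness) is open-ended, so an investigator may refuse an extreme case. It names no lipid condition or value.
- *Section 6.0* leaves management to clinical judgment. It concerns adverse drug reactions and sets no entry limit.
- *The calendar* requires no panel after the lipid drug is started. In a patient newly medicated because of the screening result, the required panel predates the drug.

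None of these reliably prevents the case.

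**5. Would a value before the first dose be out of keeping with the protocol?** No. For glucose, section 5.2.8 says "Optimal glycemic control should be achieved before starting a patient on everolimus". Exclusion item 9 sets an HbA1c limit of 8%, and section 5.2.10 starts hepatitis B prophylaxis 1-2 weeks before the first dose. These do not prove that a lipid limit is needed. They show only that one would fit.

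**6. Design.** Section 14.1 enrolls 12 patients and declares preliminary evidence of efficacy at 2 or more responders. Neither number depends on item 7h.

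**The case against.** The strongest reply is that the two provisions address different situations. The dose tables in section 6.0 are for everolimus-related toxicity, and the first of them refers grade 3 lipid events to section 5.2.8. Stopping a drug that has raised a patient's lipids says little directly about starting it in someone with treated, pre-existing dyslipidemia. The note also asks for *appropriate* medication, and a drug that leaves the patient at grade 4 arguably is not. A physician who sees a grade 4 value on day 1 can read the table in section 5.2.8 and hold the drug. Section 6.0 also has a softer row for other grade 4 events: hold until grade 1 or baseline, then restart one level lower.

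Much of this stands. A reader might infer that the protocol contradicts itself. It does not, because section 5.2.8 is on-treatment guidance subject to judgment. A reader might also infer that grade 3 patients should be barred. The documents do not support that: such a bar would be stricter than the restart rule in section 5.2.8, which names no lipid level, and it is a debatable trade-off in a small, mutation-selected trial.

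What does not stand is that the safeguards settle grade 4. The physician on day 1 may have no value taken after the lipid drug was started, since none is required. The softer row in section 6.0, if it covers lipids at all, would also stop dosing at grade 4.

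**Conclusion.** The point holds for grade 4 only, as a minor safety improvement. The stated entry rule can admit a patient still at grade 4 to 10 mg daily, and no other provision sets a limit that prevents it.

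Its size in patients cannot be given, because the documents report no frequency of grade 4 lipids at entry. A reader might infer that the efficacy conclusion is at risk; nothing in the plan supports that.

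The conclusion rests on two assumptions. The first is that the note means what it says, with initiation as the only condition. The second is that the grades in section 5.2.8 follow CTCAE version 4.0. Section 7.1.1 names that version for toxicity reporting, but section 5.2.8 names none and section 5.2.10 cites version 3.0 for recording viral reactivation and flare. The documents do not print the grade 3 and 4 lipid cut-offs, so how extreme such a patient must be cannot be judged from them.

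**What to change.** End the note in item 7h with: *and a repeat fasting lipid panel on that medication, taken before registration, shows neither cholesterol nor triglycerides at grade 4 (CTCAE version 4.0)*.

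Add to calendar footnote 5: *Repeat before registration if the 7h NOTE applies*.

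The timing matters because section 4.0 requires eligibility to be confirmed before registration, so a panel drawn just before the first dose could come too late. The CTCAE version should be named because the grade 4 cut-offs are not printed.

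The cost is one extra fasting blood test for patients above the limits and a possible short delay, whose length the documents do not allow us to state. If the delay takes the baseline evaluations past 14 days before the start of therapy they must be repeated, and past 28 days the scans as well. Rarely, a patient who stays at grade 4 on medication would be excluded, which is a real loss among 12. Patients at grades 2 and 3 remain eligible under the note, subject to clinical judgment.

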3.2 Exclusion Criteria

1. A history of other malignancy ≤ 3 years previous with the exception of basal cell or squamous cell carcinoma of the skin which were treated with local resection only or carcinoma *in situ* of the cervix.
2. Taking an investigational agent within 4 weeks of initiation of everolimus.
3. Symptomatic brain metastases. Known brain metastases are allowed if asymptomatic and previously treated.
4. A history of allergic reactions attributed to compounds of similar chemical or biologic composition to everolimus or other agents used in the study.
5. Known impairment of GI function or GI disease that may significantly alter the absorption of oral everolimus.
6. Currently taking CYP3A4 inhibitors or inducers (such as the antiepileptic drugs phenytoin, carbamazepine, or phenobarbital; cyclosporine; grapefruit or its juice; Seville oranges; starfruit; or St. John's wort) (refer to Section 5.3).

7. Chronic treatment with corticosteroids or other immunosuppressive agents. Topical or inhaled corticosteroids are allowed.
8. Received live attenuated vaccine within 1 week of start of everolimus (i.e. intranasal influenza, measles, mumps, rubella, oral polio, BCG, yellow fever, varicella, and TY21a typhoid vaccines).
9. Uncontrolled diabetes mellitus defined as HbA1c > 8% despite adequate therapy. Patients with a known history of impaired fasting glucose or diabetes mellitus may be included; however, blood glucose and antidiabetic treatment must be monitored closely throughout the trial and adjusted as necessary.
10. Uncontrolled intercurrent illness including, but not limited to, ongoing or active infection, symptomatic congestive heart failure of NYHA class III or IV, active coronary artery disease, unstable angina pectoris, cardiac arrhythmia, myocardia infraction \leq 6 months prior to start of everolimus, uncontrolled hypertension (systolic pressure > 150 mmHg or diastolic pressure > 90 mmHg), uncontrolled seizure disorder, liver disease such as cirrhosis, decompensated liver disease, active and chronic hepatitis, known severely impaired lung function (spirometry and DLCO 50% or less of normal and O₂ saturation 88% or less at rest on room air), active bleeding diathesis, or psychiatric illness/social situations that would limit compliance with study requirements.
11. Pregnant and/or breastfeeding. Women of childbearing potential must have a negative pregnancy test within 14 days of study entry.
12. Known HIV-positivity on combination antiretroviral therapy because of the potential for pharmacokinetic interactions with everolimus. In addition, these patients are at increased risk of lethal infections when treated with marrow-suppressive therapy. Appropriate studies will be undertaken in patients receiving combination antiretroviral therapy when indicated.

